Effect of confounding: The overall rate ratio can be written as: $R = c \cdot R_v + (1-c)R_u$, where R_v is the rate ratio comparing vaccinated children in implementation areas and unvaccinated children in comparator areas, and R_u is the rate ratio comparing unvaccinated children in implementation and comparator areas, and R is the overall rate ratio that we observe directly. If there is no confounding (as if vaccination essentially assigned at random), $R_u = 1$ and $R = cR_v + 1 - c$. The observed R could then be compared with expected value if R_v was equal to the rate ratio in vaccinated children in the phase 3 trial for a given value of c . If there is confounding, $R_v = (F \times R_v^*)$, $R_u = (G \times R_u^*)$, where R_v^* is the true (unconfounded) rate ratio vaccinated:unvaccinated, $R_u^* = 1$ by definition, and F and G represent the confounding, i.e. F is the factor by which the rate in the RTS,S-vaccinated is increased relative to the unvaccinated comparator population, aside from any effect of the RTS,S vaccine, and G the

factor by which the rate in those that did not receive RTSS, is increased relative to the comparator population.

Confounding with respect to malaria outcomes: Preliminary estimates from the baseline surveys in each country, during which children 5-48 months were tested for malaria infection using an RDT and receipt of routine vaccinations was recorded, there was no evidence that coverage of basic vaccines was associated with malaria prevalence, suggesting confounding with respect to malaria outcomes may not be important.

Confounding with respect to meningitis: Apart of any effect of RTSS itself, the rate of meningitis is likely to be higher in the RTSS-unvaccinated and lower in the RTSS-vaccinated, because children who receive RTSS also more likely to have had pneumococcal and Hib vaccines, which protect against meningitis, than children who did not receive RTSS, unless high levels of coverage of pneumococcal and Hib vaccines have essentially eliminated vaccine serotypes from circulation. Conservatively, if say 90% of the population received anti-meningitis vaccines, and coverage of RTSS-1 is 80%, and 84% of those who received anti-meningitis vaccines also receive RTSS-1, then coverage of anti-meningitis vaccine among those who receive RTSS-1 is 95% and 70% in those who do not receive RTSS-1:

		RTSS-1		
		Y	N	Total
Anti-meningitis vaccine	Y	760	140	900
	N	40	60	100
Total:		800	200	1000

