Coverage of pneumo-2:		760/800=0.95	140/200=0.7	900/1000=0.9

If efficacy of anti-meningitis vaccine against meningitis of any cause is 70%, then the rate in RTSS recipients (before any RTSS effect) is reduced by a factor $0.95 \times (1 - 0.7) + (1 - 0.95) = 0.335$, compared to a factor of $0.9 \times (1 - 0.7) + 0.1 = 0.37$ in the unvaccinated comparator population, a rate ratio of $0.335 / 0.37 = 0.905$. Among those who do not receive RTSS-1, the corresponding factor is $0.7 \times (1 - 0.7) + 0.3 = 0.51$, compared to 0.37 in the comparator population, a rate ratio of $0.51 / 0.37 = 1.378$:

	RTSS-1	no RTSS-1
anti-meningitis vaccine coverage:	0.95	0.7
rate of meningitis reduced by factor:	$0.95 \times (1 - 0.7) + 0.05 = 0.335$	$0.7 \times (1 - 0.7) + 0.3 = 0.51$
Comparator population:		
anti-meningitis vaccine coverage:	0.9	
rate of meningitis reduced by factor:	$0.9 \times (1 - 0.7) + 0.1 = 0.37$	
rate ratio:	$0.335 / 0.37 = 0.905$	$0.51 / 0.37 = 1.378$

The observed rate ratio comparing implementation and comparator areas is:

$R=c.(F \times R_v^*)+(1-c).G$, with $F=0.905$, $G=1.378$ in this example. If the true (unconfounded) rate ratio was $R_v^*=10.5$ (as in the phase 3), and coverage of RTSS-1 was 80%, we would expect to see a rate ratio $R=0.8 \times 0.905 \times 10.5+(1-0.8) \times 1.378=7.878$ between implementation and comparator areas. To be able to rule out an association with meningitis of the magnitude seen in the phase 3 trial we would therefore want to be able to exclude rate ratios of about 7.9 or more. This compares with a value of $0.8 \times 10.5+0.2=8.6$ if there was no confounding.

Contamination:

Contamination could occur due to:

- a) Children in comparator clusters receive the malaria vaccine (either by attending a clinic in an implementation area instead of “their own” clinic, OR by moving address, after they have been vaccinated, from an implementation to a comparator cluster), so there is some benefit (or harm) in comparator areas, diluting our estimates of impact which compare implementing and comparator clusters;
- b) Children in intervention clusters receive their vaccinations from a clinic in a comparator area (by going to the “wrong” clinic, or by moving address after completing vaccination), so coverage of the vaccine in intervention areas, is lowered;
- c) Cases or deaths, who are assigned to the wrong cluster by mistake.

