- d) Cases or deaths are assigned to the wrong age group, i.e. cases in vaccine-eligible children assigned to non-eligible age groups and cases in non-eligible age groups assigned to the vaccine eligible age group, due to error in age or date of event. And then there is also contamination whereby children outside the eligible age group, receive the vaccine.

If there is contamination due to having some vaccinated children in age-eligible groups in comparator clusters, and the proportion of vaccinated person time among vaccine eligible age groups in comparator clusters is d ,

$$R = \{ [c \times \Sigma n_v / \Sigma T_v + (1-c) \times \Sigma n_u / \Sigma T_u] \div [d \Sigma n'_v / \Sigma T'_v + (1-d) \Sigma n'_u / \Sigma T'_u] \} \times [\text{correction term}],$$

[figure not shown]
where $\Sigma n'_v$ and $\Sigma T'_v$ are the total events and person time in vaccinated children in vaccine-eligible ages in comparator clusters. Comparing this with the corresponding R without contamination, the estimate with contamination differs by a factor: $1/(d.R_v^*F'+(1-d).G')$, where R_v^* is the unconfounded rate ratio for vaccinated:unvaccinated, and F' and G' represent the confounding. If the coverage of RTSS-1 in comparator areas is 1%,

		RTSS-1		
		Y	N	Total
anti-meningitis vaccine	Y	10	890	900
	N	0	100	100
Total:		10	990	1000
coverage of anti-meningitis vaccine:		10/10=1	890/990=0.89	900/1000=0.9

[figure not shown]
RTSS-1	no RTSS-1
--------	-----------

anti-meningitis vaccine coverage:	1	0.89
rate of meningitis reduced by factor:	$1 \times (1 - 0.7) = 0.3$	$0.89 \times (1 - 0.7) + (1 - 0.89) = 0.37$
Comparator population:		
anti-meningitis vaccine coverage:	0.9	
rate of meningitis reduced by factor:	$0.9 \times (1 - 0.7) + 0.1 = 0.37$	
rate ratio:	$0.3 / 0.37 = 0.81$	$0.37 / 0.37 = 1$

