So for 90% coverage of anti-meningitis vaccine, and 1% coverage of RTSS, if all the RTSS-vaccinated received anti-meningitis vaccine, $F' = 0.81$ and $G' = 1$. If Rv^* is 10.5, and d is 1%, this gives R with contamination reduced by a factor of $1 / [0.01 \times 10.5 \times 0.81 + (1 - 0.01) \times 1] = 0.93$. If d is 2% this factor is 0.87 and 5%, 0.73. The values with no confounding are 0.91, 0.84, 0.68 for 1%, 2% and 5% contamination. So allowing for confounding in implementation areas, and contamination and confounding in comparator areas, if contamination is 1%, we would aim to exclude a target R value of $7.878 \times 0.93 = 7.3$, or for $d = 2\%$ or 5% , values of 6.8 or 5.7.

Effect of contamination on other outcomes (examples for cerebral malaria (R_v^* 2.57); mortality, 0.9, severe malaria, 0.7):

Power calculations:

Power was estimated using simulations in which the number of events in cluster j and age group k , was a random value from a poisson distribution with mean equal to $r \cdot k_{ij} y_{jkt} \theta_{jk}$, where r is the assumed underlying incidence rate, k_{ij} is an adjustment factor for the relative access to hospital i for cluster j (explained below), y_{jkt} is the person time in cluster j in age group k at time t , and θ_{jk} is the rate ratio for the outcome associated with vaccine introduction, for cluster j and age group k . $\theta_{jk} = \theta$ for vaccine-eligible age group in clusters in the intervention arm, $\theta_{jk} = 1$ otherwise. For each simulation, the ratio of the number of events between the two age groups was compared between arms using a ratio estimator. The simulation was repeated 10,000 times, to determine the distribution of the estimate of θ and of the 95% confidence limits. Simulations were done for null value ($\theta = 1$) for a range of assumed underlying incidence rates, and for various values of $\theta > 1$ (safety) and $\theta < 1$ (impact) to estimate power to detect or exclude effects of interest. Simulations were repeated for a range of values of the underlying incidence rate, for various time points, in order to determine the number of events that would be required to have adequate power, at each time point.

Relative access to hospital:

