(average for the period from vaccine introduction to Dec 2020), and estimates of the degree of contamination (% admissions (or % deaths) in vaccine-eligible age groups in comparator areas, who had received RTSS-1).

Country	Coverage of RTSS-1	Contamination (RTSS-1 coverage in comparator areas in hospital catchments)	
		from mortality surveillance (HBR or recall)	from hospital admissions (HBR or recall)
Malawi	72.3%	4.8%	2.7%
Ghana	69.0%	0.0%	5.9%
Kenya	79.8%	5.3%	4.6%
TOTAL	73.7%	3.4%	4.4%

Table 5: Power to detect or exclude effects on safety outcomes, of the magnitude observed in the phase 3 trial, and power to detect impact on hospital admission with severe malaria, and on all-cause mortality

	Effect in the phase3 trial ¹	Corresponding effect size, allowing for coverage ²	Effect size allowing for contamination ³	Effect size allowing for confounding ⁴	Number of events required for given power to detect or exclude effects of the given size ⁵	
					90% power	80% power
Safety outcomes:						
Meningitis	10.5	8.00	5.80	5.66	90	70
Cerebral malaria	2.57	2.16	2.03		400	300
Gender interaction (mortality)	1.7	1.52	1.47		2000	1500
Impact:						
Severe malaria ⁶	0.66	0.75	0.76		4000	3000
Mortality ⁷ a)	0.898	0.92	0.93		24000	18000
b)	0.864	0.90	0.90		17600	13100

1 In the phase 3 trial, the observed rate ratio for meningitis (RTS,S/AS01:control) was 10.5, and for cerebral malaria, 2.57. Among girls, there was a higher mortality rate in RTS,S/AS01 recipients than controls, the mortality ratio was 2 over the whole trial period, and was 1.7 in the first part of the trial (from enrolment until the 4th dose was administered) and 3.4 in the latter part of the trial.

2 Assuming coverage of RTSS-1 of 74% (the average value in Table 4)

3 Assuming coverage of RTSS-1 in comparator areas is 4%

4 Confounding: For meningitis, assuming RTSS-recipients more likely to have received other vaccines that would prevent meningitis (90% coverage of anti-meningitis vaccines, 50% efficacy against all-cause meningitis, all RTSS recipients have received anti-meningitis vaccine). Based on preliminary data from baseline surveys, EPI coverage did not appear to differ between high and low malaria prevalence areas, and was similar in children who tested positive for malaria infection by RDT and children who tested negative. We have therefore assumed no confounding for impact outcomes.

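### SAP Table 5 prints 5.66 as the meningitis effect size after confounding, but the inputs in its own notes give about 5.5

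*SAP*

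**What the plan says.** SAP section 8 converts the phase 3 effects into the rate ratios expected between implementation and comparator areas. For meningitis it starts from the phase 3 figure ("the observed rate ratio for meningitis (RTS,S/AS01:control) was 10.5"). Table 5 then prints 8.00 allowing for coverage, 5.80 allowing for contamination and 5.66 allowing for confounding, with 90 events for 90% power and 70 for 80% power.

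The notes to Table 5 give the inputs:

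- Note 2, coverage: "Assuming coverage of RTSS-1 of 74% (the average value in Table 4"). Table 4 prints the total as 73.7%.
- Note 3, contamination: "Assuming coverage of RTSS-1 in comparator areas is 4"%.
- Note 4, confounding: "90% coverage of anti-meningitis vaccines, 50% efficacy against all-cause meningitis, all RTSS recipients have received anti-meningitis vaccine".

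The text before the table sets out the formula and a worked example with other inputs. On efficacy it says "If efficacy of anti-meningitis vaccine against meningitis of any cause is 70"%. For implementation areas it takes 80% RTSS-1 coverage, and "coverage of anti-meningitis vaccine among those who receive RTSS-1 is 95% and 70% in those who do not receive RTSS-1". For comparator areas its factors apply "if all the RTSS-vaccinated received anti-meningitis vaccine". On contamination it says "Comparing this with the corresponding R without contamination, the estimate with contamination differs by a factor", and prints the reciprocal of the confounded, contaminated comparator rate.

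**The concern.** The confounding column holds the last adjustment to the meningitis target. Section 8 gives the purpose of that target: to be able to rule out an association as large as the one seen in phase 3, on a primary safety outcome. A reader should be able to regenerate the number from its footnote. Using the note's inputs in the SAP's formula moves the target from 5.80 to about 5.47 (at 73.7% coverage), a drop of 0.33. The printed drop is 0.14. The table therefore shows less than half of the confounding that its note implies, and nothing in the text explains the difference. At stake is whether the benchmark can be traced to its assumptions, and whether the event counts beside it belong to the value that is kept.

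**Working it through.** **Formula (SAP section 8).**

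R = [c·F·Rv + (1 − c)·G] / [d·Rv·F′ + (1 − d)·G′]

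Here c is RTSS-1 coverage in implementation areas, d is RTSS-1 coverage in comparator areas and Rv = 10.5. F and G are the meningitis rates in RTSS-1 recipients and non-recipients, before any RTS,S effect, relative to the comparator population. F′ and G′ are the same quantities in comparator areas.

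**Step 1. Check the formula on figures the SAP prints.**

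- Worked example (c = 0.80, d = 0.01, 70% efficacy): F = 0.335/0.37 = 0.905, G = 0.51/0.37 = 1.378, numerator 7.88, and 7.3 after contamination. These agree with the SAP.
- Table 5 meningitis without confounding, c = 0.737, d = 0.04: 0.737 × 10.5 + 0.263 = 8.00; divided by (0.04 × 10.5 + 0.96) = 1.38 this is 5.80. Both match. With c rounded to 0.74 they would be 8.03 and 5.82, so the table appears to use 73.7%.
- The other rows with c = 0.737, d = 0.04: cerebral malaria 2.16 and 2.03; gender interaction 1.52 and 1.47; severe malaria 0.75 and 0.76; mortality 0.92 and 0.93, and 0.90 and 0.90. All match.

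**Step 2. Apply the inputs of notes 2 to 4** (c = 0.74, d = 0.04, anti-meningitis vaccine coverage 0.90, efficacy 0.50, all recipients covered).

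- Comparator population factor: 1 − 0.90 × 0.50 = 0.55.
- F = F′ = 0.50/0.55 = 0.909.
- Coverage in non-recipients, implementation areas: (0.90 − 0.74)/0.26 = 0.615; G = (1 − 0.50 × 0.615)/0.55 = 1.259.
- Coverage in non-recipients, comparator areas: (0.90 − 0.04)/0.96 = 0.896; G′ = 1.004.
- Numerator: 0.74 × 0.909 × 10.5 + 0.26 × 1.259 = 7.391.
- Denominator: 0.04 × 10.5 × 0.909 + 0.96 × 1.004 = 1.3455.
- R = 7.391/1.3455 = **5.49**, against 5.66 printed.

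**Step 3. Vary the reading of the notes.**

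| Reading | c = 0.74 | c = 0.737 |
|---|---|---|
| As above | 5.49 | 5.47 |
| G′ set to 1, as the worked example does | 5.51 | 5.49 |
| Confounding in implementation areas only | 5.36 | 5.34 |

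The contamination totals in Table 4 do not close the gap: 3.4% gives 5.69 to 5.73 and 4.4% gives 5.34 to 5.37. The adjacent 5.80 needs 4% in any case.

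**Step 4. Look for inputs that do give 5.66.** Take the worked example's assumptions (70% efficacy, 95% of recipients covered in implementation areas, all recipients covered in comparator areas, G′ = 1) with c = 0.74 and d = 0.04.

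- Coverage in non-recipients: (0.90 − 0.74 × 0.95)/0.26 = 0.758; G = (1 − 0.70 × 0.758)/0.37 = 1.269.
- Numerator: 0.74 × 0.905 × 10.5 + 0.26 × 1.269 = 7.365.
- Denominator: 0.04 × 10.5 × 0.811 + 0.96 = 1.3005.
- R = 7.365/1.3005 = **5.66**.

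Variants of this set (exact G′, c = 0.737, or F and G held at the example's printed values) give 5.61 to 5.68. The match is not unique: 50% efficacy with 95% of recipients covered in both areas also gives 5.66.

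**Step 5. Size of the effect on events.** Assume that the 90 and 70 events belong to 5.66 and that events scale roughly as 1/(ln R)².

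- 90 × (ln 5.66/ln 5.5)² ≈ 93.
- 70 × (ln 5.66/ln 5.5)² ≈ 72.

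The SAP's counts come from simulation and are rounded, so this scaling shows only the order of the change.

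**The case against.** The strongest reply is that the number may be right and only the footnote wrong. The worked example's assumptions reproduce 5.66, so the author may have computed the cell from them and described another set in note 4. The documents leave this open, and the fix must allow for it. It does not remove the mismatch, since either the cell or the note has to change.

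A second reply is that an illustration and a table may use different inputs. The example is offered as a supposition at 80% RTSS-1 coverage, and Table 5 has its own notes. That is fair: 70% efficacy in one place and 50% in the other is not an error in itself. The point rests only on Table 5 against its own notes.

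Three stronger readings are tempting, and the documents do not support them.

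- A reader might put the example's 70% efficacy into note 4 and infer a target near 5.1. That mixes two sets: the example does not have all recipients covered in implementation areas. Its full inputs give about 5.6 to 5.7.
- A reader might infer that 30% efficacy was used by mistake, because with all recipients covered it also gives about 5.66. Neither document mentions 30%, and other sets fit equally well.
- A reader might infer that the exclusion threshold is too high in practice, so that an upper limit between 5.5 and 5.66 would wrongly count as exclusion. The SAP has no decision rule tied to 5.66. Its power statement in section 8 is for a 5-fold increase. Annex 4 describes the phase 3 signal as about 5 to 6 and sizes cases for a ratio of 5. The response to a safety signal in section 8 weighs several kinds of evidence and sets no cut-off.

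**Conclusion.** The point stands as a mismatch between a printed number and its stated inputs. Under the section 8 formula, notes 2 to 4 give 5.47 to 5.51, about 3% below the printed 5.66. Rounding does not explain it, because the coverage and contamination columns reproduce to two decimals by the same method. Which of the cell and the note is wrong cannot be settled from the documents.

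The consequence for planning is small. About 93 events in place of 90 stays inside the 80 to 100 case trigger in SAP Annex 3, and the 5-fold ratio in the power statement lies below both 5.5 and 5.66. This rests on the approximate scaling in step 5 and on reading the 90 and 70 events as belonging to the final column. It remains worth correcting because the figure is the stated counterpart of the phase 3 meningitis signal for a primary safety outcome.

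**What to change.** Choose one of two corrections to SAP Table 5:

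1. If note 4 states the intended assumptions, print 5.5 in the confounding cell.
2. If 5.66 is the intended value, rewrite note 4 with the inputs that produce it: anti-meningitis vaccine coverage overall and among RTSS-1 recipients in each type of area, efficacy, and whether G′ is set to 1.

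In either case, state whether 73.7% or 74% coverage is used, add a sentence on why the table's assumptions differ from the worked example if they do, and confirm the 90 and 70 event counts against the value kept. The cost is a text correction and, if wanted, one rerun of the existing simulation. Design, data collection and analysis timing do not change.

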Table 1: Number of clusters randomized in each country, number of surveillance hospitals, and the number of clusters within the catchment of the sentinel hospitals

Country	Clusters	Population: annual birth cohort mean (range)	Sentinel Hospitals	Clusters in sentinel hospital catchments	Catchment clusters: annual birth cohort mean (range)
Ghana	66	3975 (912,8954)	8	32	4628 (1202,8954)
Kenya	46	5488 (2702,10739)	6	28	5559 (3487,10739)
Malawi	46	4820 (2816,8112)	4	17	5115 (2816,8112)
TOTAL	158	4661	18	77	5074

(excludes areas where the GSK phase 4 study is being done in each country)

Hospital and mortality surveillance will start when RTS,S/AS01 vaccination begins, or as soon as possible after that date, and be maintained until 46 months from the start of RTS,S/AS01 vaccination.

Administration of doses of RTS,S/AS01 and of other vaccines will be recorded by the EPI programme in each country using their normal record keeping system. Vaccination coverage will also be measured independently through community surveys. A survey will be undertaken at baseline, to measure coverage of EPI vaccines and Vitamin A, deworming treatment, malnutrition by MUAC, and the prevalence of *P.falciparum* infection (using an HRP2 Rapid Diagnostic Test). A second survey will be undertaken after about 18 months to measure coverage of EPI vaccines and, in RTS,S clusters, coverage of 1,2 and 3 doses of RTS,S in children 12-23 months of age. A third survey is planned to measure coverage of the fourth dose of RTS,S.

The MVPE was designed to detect differences in disease and mortality rates, over 46 months, between RTS,S and comparison clusters. Specifically, it was powered to detect a reduction in all-cause mortality in each country in RTS,S clusters of 10% or more (with 90% power) ; to detect a 2.6-fold or greater increase in the rate of meningitis (all countries combined) with 90% power ; to detect an increased incidence of cerebral malaria if the true rate is increased by 1.7-fold or more; and to detect an increase in the female:male mortality ratio with 90% power if the ratio is increased by 1.15-fold or more.

3. Description of the clusters

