5 The number of events required for given power. The numbers refer to the total events in eligible and non-eligible groups combined, except for the interaction by gender, where the number refers to the number of deaths in vaccine-eligible ages.

[figure not shown]
6 Efficacy of RTS,S/AS01 against severe malaria, during the first 20 months of the trial (ITT analysis) was 34% (rate ratio 0.66).

7 The expected reduction in all-cause mortality is a) 10.2%, if efficacy against malaria deaths is 34%, and the percentage of deaths caused by malaria (in the absence of the vaccine) is 30%. This translates to a 7% reduction after allowing for 74% coverage and 4% contamination. If the percentage of deaths caused by malaria is 40% (b), the expected reduction in all-cause deaths is 14%, which translates to a 10% reduction at population level.

Further details of power simulations, including predicted distribution of point estimates of effects, are given in Annex 4. Based on incidence rates of the key outcomes observed during the first 12 months of surveillance, we estimated that by the end of month 24 (April 2021), sufficient events would be expected to have accrued to give 90% power to detect or exclude a 5-fold increase in incidence of hospital admission with meningitis associated with introduction of RTS,S/AS01, and at least 80% power to detect a 2-fold increase in incidence of hospital admission with cerebral malaria, and 90% power to detect a 1.4-fold relative increase in all-cause mortality in girls compared to boys associated with RTS,S/AS01 introduction, in pooled analysis across the three countries. By this time point, there would also be good power to detect a reduction in the incidence of hospital admission with severe malaria. There would be low power to detect reductions in all-cause mortality at this time point, but it is anticipated that sufficient events would have accrued by the end of the evaluation (month 46 in each country) to have 90% power to detect a reduction of 10% and 80% power to detect a reduction of 8%.

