Annex 4: Estimates of the power of the evaluation, from simulations

A4.1 Predicted range of point estimate for the meningitis incidence rate ratio between RTS,S/AS01 and comparator areas, assuming no effect of RTS,S/AS01 on meningitis.

A4.2 Predicted range of the upper 95% confidence limit for the meningitis incidence rate ratio between RTS,S/AS01 and comparator areas, assuming no effect of RTS,S/AS01 on meningitis.

Predictions of the range of the upper 95% confidence limit for the meningitis rate ratio, if

[figure not shown]
- the rate of admission with meningitis is 0.02/1000,
- assuming no effect of RTS,S/AS01
- data for 3 countries combined,

by months after start in first country

Smallest rate ratio the study would allow us to exclude:

Month	Power	
	80%	90%
12	24.7	34.6
15	17.0	29.9
18	10.5	18.3
21	7.4	11.2
24	5.8	8.2
27	4.8	6.4
30	4.2	5.4
33	3.7	4.7
36	3.4	4.2
39	3.2	3.9
42	3.0	3.7
45	2.9	3.5

A4.3 Predicted range of point estimates for the ratio of female:male mortality ratios between RTS,S/AS01 and comparator areas, assuming no differential effect of RTS,S/AS01 on survival of boys and girls.

[figure not shown]
Comparison of female:male mortality ratio between RTSS/AS01 and comparator areas:

Predictions of the range of point estimates of the ratio of mortality ratios, assuming:

- mortality 2/1000 (5-23 mths), decreasing with age
- no differential effect of RTS,S/AS01
- data for 3 countries combined by months after start in first country

nA – no. deaths girls
 nB – no. deaths boys
 among vaccine-eligible age groups

A4.4 Predicted range of the upper 95% confidence limit for the ratio of female:male mortality ratios between RTS,S/AS01 and comparator areas, assuming no differential effect of RTS,S/AS01 on survival of boys and girls.

Comparison of female:male mortality ratio between RTSS/AS01 and comparator areas:

Predictions of the range of the upper 95% confidence limit for the ratio of mortality ratios

nA – no. deaths girls
nB – no. deaths boys
among vaccine-eligible age groups

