For meningitis, the 10-fold increase in risk in vaccinated children observed in the phase 3 trial, would correspond to a rate ratio of about 5 to 6 after allowing for expected levels of coverage and contamination. The minimum number of cases required for 90% power to detect an increase in incidence due to RTS,S introduction, if the true rate ratio is 5, is about 80 to 100 cases in the vaccine-eligible and non-eligible age groups combined, Figure A4.5. (The number of events needed, is not the same at each time point, because the power depends on the relative number of cases in vaccine-eligible and non-eligible age groups and is optimal when these are equal).

Figure A4.5. Number of meningitis cases required for 90% power to detect a 5-fold increase in incidence due to RTS,S introduction, for analyses at different timepoints.

[figure not shown]
[figure not shown]

Figure A4.6. Number of meningitis or cerebral malaria cases required for 90% power to detect a 2- to 5-fold increase in incidence due to RTS,S introduction (for an analysis at the end of the evaluation).

In the phase 3 trial, among girls, mortality was 2-fold higher in those who received RTS,S/AS01 than in those who received the control vaccine (risk ratio 2.0), while among boys, mortality was lower in those who received RTS,S/AS01 (risk ratio 0.76), giving a ratio of mortality ratios of 2.62. This gender difference appeared stronger in the latter part of the trial, when, among girls, mortality was 3.4-times higher in RTS,S recipients than controls, while in boys mortality was slightly lower (risk ratio 0.88), giving a ratio of mortality ratios of 3.84.

Mortality ratios in the phase 3 trial

	Whole period	0-20mths	21+mths
Mortality risk ratio girls:boys, RTS,S group	1.50	1.75	1.12
Mortality risk ratio girls:boys, control group	0.57	0.72	0.29
Ratio RTS,S:control	2.62	2.43	3.84
Ratio of mortality risk RTS,S:control, in girls	2.00	1.70	3.40
Ratio of mortality risk RTS,S:control, in boys	0.76	0.70	0.88
Ratio girls:boys	2.62	2.43	3.84

(These risk ratios are approximately equal to mortality rate ratios)

If RTS,S/AS01 coverage in the MVPE is 60% in both boys and girls, a ratio of mortality ratios of 2.6 translates to a ratio, at population level, of 1.9. A ratio of 2.0 among RTS,S recipients would translate to a ratio of 1.6, and a ratio of 1.5 to a ratio of 1.3.

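### At the only incidence rate printed with a month-by-month table, power to exclude a 5-fold meningitis increase at month 24 is below 80%, not 90%; the 90% for detecting 2.6-fold disagrees with protocol 10.10

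*SAP*

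**What the plan says.** **Month 24.** The subsection of SAP Section 8 on power to detect or exclude effects states that "by the end of month 24 (April 2021), sufficient events would be expected to have accrued to give 90% power". For meningitis, pooled over the three countries, the claim is "90% power to detect or exclude a 5-fold increase in incidence of hospital admission with meningitis" by April 2021. The basis is given as "Based on incidence rates of the key outcomes observed during the first 12 months of surveillance", but neither a meningitis rate nor an expected case count is printed. The preceding sentence refers to Annex 4 for details.

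**Annex 4.** A4.2 assumes no vaccine effect, three countries combined, months counted from the first country's start, and that "the rate of admission with meningitis is 0.02/1000". Its table is headed "Smallest rate ratio the study would allow us to exclude". The text after the A4 tables says that the number of cases needed for 90% detection of a 5-fold increase "is about 80 to 100 cases in the vaccine-eligible and non-eligible age groups combined".

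**Table 5.** The meningitis row reads "Meningitis 10.5 8.00 5.80 5.66 90 70": 90 events for 90% power and 70 for 80%, at a diluted ratio of 5.66.

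**2.6-fold.** SAP Section 2 says that the evaluation was powered "to detect a 2.6-fold or greater increase in the rate of meningitis (all countries combined) with 90% power". The Study Size entry of the protocol abstract also says 90%. Protocol 10.10 says 80% for the same effect.

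**The concern.** Detecting a true 5-fold increase and excluding one when the vaccine has no effect are different tasks. Exclusion is the harder one here, because without an effect there are fewer cases in the vaccine-eligible group. Section 8 gives both the same 90%, while the annex table for exclusion gives a weaker figure at the same month.

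Exclusion is what a reassuring result would rest on. Section 8 sets the aim of ruling out an association of the size seen in phase 3. Section 1 expects enough safety data after about two years and allows a recommendation before the final impact data. If a null result at month 24 were read as having 90% power to exclude 5-fold when the true figure was nearer 70%, a primary safety outcome would look better resolved than it is.

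**Working it through.** **1. Reading A4.2 directly (no modelling).** Smallest excludable ratio:

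| Month | 80% power | 90% power |
|---|---|---|
| 24 | 5.8 | 8.2 |
| 27 | 4.8 | 6.4 |
| 30 | 4.2 | 5.4 |
| 33 | 3.7 | 4.7 |
| 45 | 2.9 | 3.5 |

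At month 24 even the 80% column is above 5. The 90% column passes 5 between months 30 and 33.

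**2. Back-calculation from the table.** SE = ln(ratio)/(1.96 + z for the power).
- Month 24, 90% column: ln 8.2/3.2415 = 0.649
- Month 24, 80% column: ln 5.8/2.8016 = 0.627
- Power to exclude 5-fold = Φ(ln 5/SE − 1.96): Φ(0.52) = 70% and Φ(0.61) = 73%
- SE needed for 90%: ln 5/3.2415 = 0.497

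**3. Simulation on the SAP design.** Inputs from the SAP: 77 catchment clusters and birth cohorts (Table 1), Poisson counts and a ratio estimator (Section 8), t-based 95% limits (Section 20). Assumptions: 0.02/1000 is per child-year and is the catchment average, cluster sizes are log-normal, and Kenya starts five months late.

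This reproduces A4.2 closely:
- Month 24: 5.4–5.6 and 7.5–7.8 (printed 5.8 and 8.2)
- Month 30: 4.0–4.1 and 5.2 (printed 4.2 and 5.4)
- Month 33: 3.7 and 4.6 (printed 3.7 and 4.7)
- Month 45: 2.8 and 3.3 (printed 2.9 and 3.5)

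A second set-up with slightly different eligibility windows gave 6.2 and 8.8 at month 24, so the printed values lie between the two. Results at 0.02/1000:

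| Quantity | One ratio over all clusters | Country estimates combined (Section 20) |
|---|---|---|
| Exclude 5-fold, month 24 | 71–76% | 63% |
| Detect 5-fold, month 24 | 93–94% | 82–83% |
| Detect 2.6-fold, months 45–46 | 85% | 83–84% |

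With follow-up to Kenya's own month 46, detection of 2.6-fold is about 88%. With no effect, about 68 cases are expected by month 24. That is just under the 70 events that Table 5 gives for 80% power at 5.66, so Table 5 and A4.2 agree with each other.

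**4. Rate needed for 90% exclusion of 5-fold at month 24.** With one ratio over all clusters, exclusion power is 83% at 0.025/1000, 90% at 0.030/1000 (about 102 cases with no effect) and 93% at 0.035/1000. In the second set-up 0.030/1000 gave 87%, or 84% with country estimates combined, so 0.03 is towards the low end of what is needed.

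**5. The 2.6-fold design figure.** Hayes–Bennett: c = 1 + (z₁ + z₂)² × Q, with Q = [(λ₀ + λ₁)/y + K²(λ₀² + λ₁²)]/(λ₁ − λ₀)². Inputs from protocol 10.10: λ₀ = 0.0004, λ₁ = 2.6 × 0.0004 = 0.00104, K = 0.4, y = 4,000 per cluster, 12 clusters per arm.
- Q = (3.60×10⁻⁷ + 1.99×10⁻⁷)/4.096×10⁻⁷ = 1.364
- 80% power: 1 + 7.849 × 1.364 = 11.7, so 12 per arm, which reproduces 10.10
- 90% power: 1 + 10.507 × 1.364 = 15.3, so 16 per arm
- Power with 12 per arm: Φ(√(11/1.364) − 1.96) = Φ(0.88) = 81%

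Using the 23,134 person-years per cluster from protocol 9.5 instead gives 98.6%. Neither input yields 90%.

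**The case against.** The strongest reply is that Section 8 does not rest on 0.02/1000. It cites observed rates, and a rate near 0.03/1000 would roughly deliver the stated exclusion power. That stands: the documents do not show the claim to be false. They leave its key input unprinted, beside an annex table that does not support it.

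Timing is also event-driven. Annex 3 triggers the meningitis analysis at 80–100 cases, and protocol 10.12 ties it to adequate power. At 0.02/1000 with no effect, about 68 cases are expected by month 24, so the rule would delay the analysis. This softens the consequence, but it does not support the month-24 date at that rate.

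Three stronger readings are tempting and are not supported:
- **That 8.2-fold refutes the whole month-24 claim.** A4.2 concerns exclusion only. At the same rate, detection of 5-fold is about 82–94%.
- **That 3.5-fold at month 45 shows 2.6-fold is out of reach.** Section 2 claims detection, and A4.2 tabulates exclusion under no effect. Like for like, detection is about 83–88%, a small shortfall. A4.2 also stops at month 45 from the first country's start, whereas the final analysis waits for month 46 everywhere.
- **That A4.2 is the only meningitis simulation.** Table 5 and Figures A4.1, A4.5 and A4.6 also report results. The figures could not be read for this check. A4.2 is the only month-by-month meningitis table with its assumed rate in the text.

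**Conclusion.** The point holds for the exclusion part of the month-24 claim, conditionally on the rate. At 0.02/1000, power to exclude 5-fold is below 80% on the annex's own figures, and about 63–76% by back-calculation or simulation, against 90% stated. It reaches 90% six to nine months later than claimed. The lower end comes from combining country estimates as in Section 20. A4.2 itself matches a single ratio over all clusters.

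This takes 0.02/1000 as a catchment average per child-year. If it applied only to each hospital's own cluster, with lower access elsewhere, month-24 exclusion would be about 58% and detection about 80%, but that version does not reproduce A4.2.

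The 2.6-fold mismatch needs no assumption about the annex rate. The documents give both 80% and 90% for one effect, and only 80% follows from the protocol's inputs, reading y as 4,000 per cluster.

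**What to change.** 1. In SAP Section 8, print the observed meningitis rate with its time unit, and the expected cases at months 24 and 46.
2. Re-run A4.2 at that rate, say whether the estimator is a single ratio or combined by country, and restate Section 8 with detection and exclusion power given separately. If the rate is near 0.02/1000, state that 5-fold can be excluded with 90% power only from about months 30–33.
3. In SAP Section 2 and the protocol abstract, change the power for 2.6-fold to 80% to agree with protocol 10.10, or show the calculation that gives 90%. Do not substitute A4.2's 3.5-fold, which is an exclusion figure.

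The cost is one simulation re-run and a few lines of text. No data collection or analysis method changes. The downside is that the stated power becomes slightly less favourable.
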